The efficacy and safety of caplacizumab in the treatment of acquired TTP have been evaluated in trial ALX-0681-2.1/10 comparing it to placebo when added to daily PE and in the 30-day post-daily PE period. The trial was terminated early due to recruitment challenges, with a total of 75 subjects enrolled and included in the intent-to-treat (ITT) analysis, but nonetheless demonstrated a statistically significant treatment effect as evidenced by the primary endpoint "time to confirmed platelet count normalization", with a hazard rate ratio (95% CI) for the caplacizumab versus placebo groups of 2.2 (1.3, 3.8), p-value for the stratified log-rank test of p=0.0048. This corresponded to a reduction in median time to confirmed platelet count normalization from 4.8 (3.6, 5.9) days in the placebo treatment group to 3.0 (2.8, 3.9) days in the caplacizumab treatment group.

The secondary endpoints illustrate the potential protective effect of caplacizumab treatment in the acute phase of TTP.

- Complete remission following initial daily PE was observed in a much higher number and proportion of subjects who received caplacizumab compared with the placebo group (29 [80.6%] subjects versus 18 [46.2%] subjects, respectively).
- A lower proportion of subjects with an exacerbation during treatment of 8% (n = 3) for caplacizumab compared to 28% (n = 11) for placebo.
- When the 1-month FU is also considered, a similar number and proportion of subjects had an exacerbation of TTP and/or a relapse of TTP (10 [27.8%] subjects in the caplacizumab treatment group and 11 [28.2%] subjects in the placebo treatment group). This suggests that in a number of subjects, the underlying auto-immune activity had not sufficiently resolved. Immunosuppressive treatment was not standardized and the shorter duration of PE in the caplacizumab arm may also have impacted the timing of the resolution of the underlying auto-immune disorder.

- The mean number of PE days during the initial daily PE period was lower in the caplacizumab group compared with the placebo group (5.9 versus 7.9, respectively), as was the mean total volume of PE administered (19923 mL versus 28307 mL, respectively).

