Platelet count is considered to be a valid measure of (potential) morbidity caused by microvascular thrombosis in the absence of a direct and/or feasible measure of the latter. Thrombocytopenia is present in all patients by definition. Platelet count normalization is the primary factor in the decision to stop daily PE treatment [19, 27]. The increase in platelet counts is also an important measure for the responsiveness to standard of care treatment. The diagnosis of a patient as having primary refractory TTP is based on an 'inadequate platelet response' over a variable observation period (e.g., 4 – 10 days) which depends on local clinical practice [28]. For example, a single center retrospective review of 64 patients with a clinical diagnosis of TTP identified a platelet count response rate of $5 \times 10^9/L$ per 24 hours over the first 3 days of PE treatment to be a predictor of sustained remission after PE and of survival [29]. The results of the TITAN trial demonstrated a more rapid return to normal platelet counts when caplacizumab was given in conjunction to daily PE, compared to placebo plus daily PE (approx. 40% improvement in time to confirmed platelet normalization) as noted in section 1.2.4.

Clinical endpoints related to disease presentation such as neurological impairment or myocardial ischemia are not suitable as a primary endpoint since they are not sufficiently characteristic of TTP. Patients present with a very variable set of signs and symptoms. There is also no standardized set of criteria or scoring system to measure the clinical severity of the disease presentation on which a clinical endpoint could be based. Biomarkers of tissue ischemia are similarly also variable in TTP patients: LDH may be seen as an overall marker of tissue ischemia, serum creatinine of renal impairment and cardiac troponin levels for cardiac ischemia but not all patients will have each biomarker elevated, further reducing the patient population if this were to become an eligibility criterion. These elements are nonetheless all important in understanding the overall treatment effect and are therefore included as secondary endpoints.

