4.3.6 Presentation of treatment groups

The following treatment group labels will be used in the tables, listings and figures, unless specified otherwise:

- Caplacizumab
- Placebo
- Open-label (OL) Caplacizumab

Treatment groups Caplacizumab and Placebo refer to the initial treatment group prior to a potential switch to open-label caplacizumab, and only data up to the switch are used in the analyses of these treatment groups. The OL Caplacizumab treatment group will only be used for analyses after the switch to open-label caplacizumab.

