4.4 Analysis Periods and Visit Windows

4.4.1 Analysis periods

The following analysis phases are defined for this study: Screening, Treatment, Follow-up. Within these analysis phases, the following analysis periods and subperiods will be considered:

Table 1: Analysis periods

Period	Subperiod	Start period	End period
(Screening)		Date of signing the ICF, with 00:00 added as timepart	First DB treatment administration datetime – 1 min
Double-Blind (DB) Treatment	Daily PE	First administration datetime of DB treatment	Start of DB post-daily PE subperiod – 1 min
	Post-daily PE	Date of switch to post-daily PE + 1 day with 00:00 added as timepart	Min(Week 5 visit date if no treatment extension or last visit date of treatment extension period with 23:59 added as timepart, early termination visit date with 23:59 added as timepart, first administration datetime of OL treatment – 1 min)
	Daily PE	First administration datetime of OL treatment	Start of OL post-daily PE subperiod – 1 min

CONFIDENTIAL

Open-label (OL) Treatment	Post-daily PE	Date of switch to post-daily PE + 1 day with 00:00 added as timepart	Min(Week 5 visit date if no treatment extension or last visit date of treatment extension period, early termination visit date) with 23:59 added as timepart
(Follow-up)		End of treatment period + 1 min	Trial termination date, with 23:59 added as timepart

Note that the last analysis period in case of early termination will always be ended by the trial termination date.

The 'overall treatment period' corresponds with the treatment analysis phase and covers both the DB treatment analysis period and the OL treatment analysis period. Note that only subjects who experience a relapse or exacerbation will have an OL treatment analysis period. For these subjects, the overall treatment period starts at start of DB treatment period and ends at end of OL treatment period. For subjects with no switch to open-label caplacizumab, the overall treatment period starts at start of DB treatment period and ends at end of DB treatment period.

The 'overall study period' covers both the treatment analysis phase and the follow-up analysis phase.

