6.2.2 Other secondary efficacy endpoints

Other secondary efficacy endpoints are defined in Section [3.3.2.2](#).

In general, all endpoints will be summarized using descriptive statistics such as number of observations, means, standard error, and proportions, as appropriate. All analyses will be run on the ITT population.

- Proportion of subjects with at least one treatment-emergent major thromboembolic event (e.g., myocardial infarction, cerebrovascular accident, pulmonary embolism or DVT), confirmed after adjudication, as well as the number of such events, during the overall treatment period (including extensions) (Caplacizumab, Placebo, OL Caplacizumab).
- Proportion of subjects with recurrences of TTP as well as the number of such events during study drug treatment (including extensions) and after study drug treatment (during FU) will be summarized by treatment group (Caplacizumab, Placebo, OL Caplacizumab).
- Proportion of subjects with treatment-emergent clinically significant TTP-related events, as well as the number of such events in the overall study period (including 4-week FU period) as defined in Section [3.3.2.2](#) will be summarized by treatment group (Caplacizumab, Placebo, OL Caplacizumab).
- Area under the curve (AUC) of platelet count until Day 5, truncated at $150 \times 10^9/\text{L}$ if platelet count is $150 \times 10^9/\text{L}$ or above, will be summarized by treatment group (Caplacizumab, Placebo). The AUC value will be calculated using the linear trapezoidal rule, i.e. $AUC_{t_i \text{ to } t_{i+1}} = 1/2 * (C_i + C_{i+1}) * (t_{i+1} - t_i)$ where C_i is the platelet count at time point t_i . Missing platelet counts will not be imputed separately as missing values can be bridged by using the trapezoid rule on neighboring (available) timepoints, thereby implicitly interpolating the missing timepoint. If the subject discontinued prior to Day 5, the subject will not be considered in this analysis. Descriptive statistics will include the 25%, 75% and 90% percentiles.
- Mortality rate (number and percentage) will be summarized by treatment group (Caplacizumab, Placebo, OL Caplacizumab) during DB treatment daily PE period (OL Caplacizumab not applicable), overall treatment period, FU period and overall study period.
- Organ damage markers:
 - Time to LDH $\leq 1 \times \text{ULN}$
 - Time to cTnI $\leq 1 \times \text{ULN}$
 - Time to serum creatinine $\leq 1 \times \text{ULN}$

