A separate KM analysis for each organ damage marker will be conducted with time to first normalization as dependent variable and treatment group (Caplacizumab, Placebo) as independent variable. Subjects in either initial treatment arm who have switched to open-label caplacizumab before having reached the endpoint will be censored at time of switch.

Time to first normalization of *organ damage marker* is defined as: first time of *organ damage marker* \leq ULN - time of first i.v. loading dose of study drug after randomization + 1 minute. All on-treatment records during DB treatment period will be used. The time to first normalization will be represented by number of days with two decimal digits.

- Proportion of subjects with increases in organ damage markers (cTnI and serum creatinine) above $1 \times$ ULN will be summarized by treatment group (Caplacizumab, Placebo, OL Caplacizumab) during DB treatment daily PE period (OL Caplacizumab not applicable), overall treatment period, FU period and overall study period.
- AUC of cTnI above $1 \times$ ULN (cTnI peak) will be summarized by treatment group (Caplacizumab, Placebo, OL Caplacizumab) during DB treatment daily PE period (OL Caplacizumab not applicable) and during overall treatment period. The AUC value will be calculated by the linear trapezoidal rule. The analysis will be repeated including and excluding cTnI peaks at baseline. Descriptive statistics will include the 25%, 75% and 90% percentiles.
- Proportion of subjects with neurological symptoms based on neurological assessment on Day 1, 2, 3, 4, 5 and Weeks 1 and 5 of 30-day post-daily PE treatment period, and the first and final FU visit will be summarized by treatment group (Caplacizumab, Placebo, OL Caplacizumab).
- Actual value and change from baseline in Standardized mini mental state examination (SMMSE) total score on Days 1, 2, 3, 4, 5 and Weeks 1 and 5 of the 30-day post-daily PE treatment period, and the first and final FU visit will be summarized by treatment group (Caplacizumab, Placebo, OL Caplacizumab). For the OL Caplacizumab treatment group change from baseline is based on the Day 1 assessment of the open-label treatment period.
- Proportion of subjects with evidence of cardiac ischemia and/or arrhythmia/conduction abnormalities on Days 1, 2, 3, and 4, and Weeks 1 and 5 of 30-day post-daily PE treatment period, and the first and final FU visit will be summarized by treatment group (Caplacizumab, Placebo, OL Caplacizumab).

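### One of the two cTnI AUC windows ends when daily plasma exchange stops, so where troponin is still raised at that point the same curve can give a smaller AUC on caplacizumab

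*SAP*

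**What the plan says.** SAP 6.2.2 plans a summary by treatment group of the cTnI area above 1 x ULN "during DB treatment daily PE period (OL Caplacizumab not applicable) and during overall treatment period", repeated with and without peaks present at baseline. On the calculation it says only that "The AUC value will be calculated by the linear trapezoidal rule". It gives no common end day and no standardisation for time.

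Table 1 in SAP 4.4.1 sets the limits of the double-blind daily PE subperiod. It opens at "First administration datetime of DB treatment" and closes one minute before the post-daily PE subperiod, which itself starts at "Date of switch to post-daily PE + 1 day with 00:00 added as timepart". The day on which daily PE stops therefore fixes the end of the window.

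For the overall treatment period, SAP 4.3.6 states for the Caplacizumab and Placebo groups that "only data up to the switch are used in the analyses of these treatment groups".

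The same section of the SAP handles platelets differently: "Area under the curve (AUC) of platelet count until Day 5", with missing values bridged by the trapezoid between neighbouring samples.

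**The concern.** A trapezoidal area grows with the length of its window for as long as the marker is above the threshold. Protocol 3.1.2 says "Platelet count normalization is the primary factor in the decision to stop daily PE treatment", and faster platelet recovery is the effect the trial is powered to show. Phase II has already shown the consequence: "The mean number of PE days during the initial daily PE period was lower in the caplacizumab group" (Protocol 1.2.4). The drug can therefore shorten the period over which troponin excess is added up, without changing troponin at all.

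Protocol 1.1 argues that more rapid reduction of cardiac ischaemia, with troponin as an example of a measure, could be expected to bring clinical benefit. A lower area on caplacizumab may then be taken as cardiac protection when part of it is shorter accumulation time.

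**Working it through.** **Inputs from the documents**
- Phase II mean PE days: 5.9 caplacizumab, 7.9 placebo (Protocol 1.2.4), used here as stand-ins for window length.
- Planning medians to platelet response: 4.2 and 7 days (SAP 3.2). Daily PE continues for at least 2 days after recovery (Protocol 3.1.1), giving 6.2 and 9.0 days.
- Study drug for 30 days after daily PE (Protocol 3.3).
- Phase II exacerbations on treatment: 8% caplacizumab, 28% placebo (Protocol 1.2.4).

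**Assumed, because the documents are silent:** the cTnI curves and the day of exacerbation.

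**The plan's own figure.** None is given for the cTnI AUC. The figure that bears on window length is the planning effect, and it reproduces: 7 x 0.6 = 4.2 days, and 4(1.960 + 0.842)²/(ln 0.6)² = 31.4/0.261 ≈ 120.3, rounded up to the stated 121 events.

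**Daily PE window, flat excess.** The area is excess x T, so the caplacizumab/placebo ratio is 5.9/7.9 = 0.75, or 25% less. With planning medians plus 2 days it is 6.2/9.0 = 0.69, or 31% less.

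**Daily PE window, falling curve.** Let cTnI = P·2^(−t/h) in multiples of ULN. It reaches ULN on day h·log2(P). With k = ln 2/h and u the smaller of T and that day, the area above ULN is P(1 − e^(−ku))/k − u. For P = 10 and h = 3 it is 26.31 at T = 5.9 and 28.41 at T = 7.9, a ratio of 0.93. Other ratios at 5.9 against 7.9 days:

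| Start (x ULN) | h = 1 d | h = 2 d | h = 3 d | h = 5 d |
|---|---|---|---|---|
| 2.5 | 1.00 | 1.00 | 1.00 | 0.99 |
| 5 | 1.00 | 1.00 | 0.99 | 0.89 |
| 10 | 1.00 | 0.995 | 0.93 | 0.86 |
| 50 | 1.00 | 0.94 | 0.89 | 0.84 |

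A curve that peaks late falls outside this range. An assumed peak of 5 x ULN on day 6 gives 7.63 against 14.38, a ratio of 0.53.

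**Overall treatment window, flat excess.** Before any switch the ratio is 35.9/37.9 = 0.95. If a fraction q switches d days after PE, the mean window is PE days + 30(1 − q) + qd:
- d = 5: (5.9 + 27.6 + 0.4)/(7.9 + 21.6 + 1.4) = 33.9/30.9 = 1.10
- d = 10: 34.3/32.3 = 1.06
- d = 15: 34.7/33.7 = 1.03

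The placebo window is now the shorter one. If cTnI normalises before daily PE stops and before any switch, the ratio is 1.00.

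**Would dividing by days help?** Take identical curves that normalise before any switch, so the total areas are equal. The mean of area/days is then proportional to (1 − q)/(PE days + 30) + q/(PE days + d):
- d = 5: (0.92/35.9 + 0.08/10.9)/(0.72/37.9 + 0.28/12.9) = 0.0330/0.0407 = 0.81
- d = 10: 0.0307/0.0346 = 0.89
- d = 15: 0.0295/0.0312 = 0.94

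Division thus turns a true ratio of 1.00 into an apparent benefit of 6% to 19% for caplacizumab. In the daily PE window it errs the other way: for P = 10 and h = 3, 26.31/5.9 = 4.46 against 28.41/7.9 = 3.60, a ratio of 1.24.

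**Common fixed window.** Identical curves over identical limits give a ratio of 1.00, whatever day PE stops.

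**The case against.** The best answer is that the endpoint counts only the area above ULN. Once cTnI is normal, further PE days add nothing, and many of the assumed curves above show no difference at all. That stands, and it is why the shortfall has to be given as a range that starts at zero.

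Second, this is an other secondary endpoint. SAP 6.2.1 confines confirmatory testing to the key secondary endpoints, so no formal conclusion depends on it. That stands too.

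Third, other planned cTnI summaries do not end when PE stops: the Kaplan-Meier time to cTnI at or below ULN, the values by time point (Table 14.2.1.3.7) and the fourth key secondary endpoint. Period durations (Table 14.1.1.5), time to stop of daily PE and number of PE days are also planned. A careful reader can therefore see the unequal windows. These outputs give context but do not repair the AUC.

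Fourth, Day 5 may not be sampled in everyone. Phase II median time to normalization on caplacizumab was 3.0 days; with at least 2 more days of PE, stopping near Day 5 may be common. After PE stops, markers are taken one day later and then about weekly. This stands in part: some subjects will need interpolation, as the SAP already accepts for platelets.

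**Conclusion.** The point holds for the daily PE window. Its end is a treatment outcome, the area is cumulative, and for identical curves the artefact can only favour caplacizumab. At the Phase II PE durations the size is 0% to about 25% for flat or falling curves, and 31% for a flat excess at the planning medians plus 2 days. These figures rest on assumed curves and on mean PE days standing in for window length.

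A reader might infer three stronger things that the documents do not support:
- That the same curve always yields a smaller area on caplacizumab. It does so only if cTnI is still above ULN when PE stops in the shorter window.
- That both windows flatter the drug. In the overall treatment window, truncation at the switch falls mainly on placebo, and for a flat excess the ratio becomes 1.03 to 1.10, against caplacizumab.
- That an observed reduction would be wholly artefact. Without a cTnI time course this cannot be said.

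The consequence is limited to how a descriptive, supportive cardiac result is read.

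**What to change.** In SAP 6.2.2 and Table 14.2.1.3.6, replace the double-blind daily PE window for the cTnI AUC with a fixed window from first dose to Day 5, the same in both arms. For subjects who stop PE before Day 5, interpolate linearly between available samples, as for the platelet AUC.

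Keep the overall-period AUC as planned, do not divide it by days covered, and cross-refer it to the period durations in Table 14.1.1.5 so that the unequal windows are visible beside it.

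The cost is a change of SAP wording and one line of the derivation. This AUC is listed in SAP 3.3.2.2 but not among the endpoints in Protocol 3.6.4, so the protocol's endpoint list does not need to change. There are two downsides. Excess after Day 5 will appear only in the overall-period AUC. For a convex fall, straight-line bridging across a sampling gap will also slightly overstate the area in early stoppers.

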In case a subject has a first or subsequent TTP relapse after completing study drug treatment in the FU period, standard of care treatment of daily PE and appropriate immunosuppressive treatment should be initiated as per site practice. There will be no re-initiation of study drug administration.

As stated above, there will be no re-initiation of study drug administration for subjects experiencing more than one exacerbation or relapse (or an exacerbation after a relapse or a relapse after an exacerbation).

[figure not shown]

Figure 3: Overview of the study design

Estimated Study Duration

The anticipated study duration per subject is approximately 2 months in case of no treatment extensions and no exacerbations and up to approximately 6 months in case of treatment extension and exacerbation during the 30-days post-daily PE period or relapse during treatment extension. The end of the study is defined as the last visit of the last subject participating in the study.

Determination of Sample Size

The hypothesis of interest in this study is to test the superiority of caplacizumab compared to placebo with respect to the time to platelet count response (initial platelet count $\geq 150 \times 10^9/L$ with subsequent stop of daily PE within 5 days). The required sample size is calculated to obtain a power of at least 80% to detect a significant reduction in time to platelet count response using a two-sided Log-rank test, at a significance level of 5%. The accrual period is taken to be 2.5 years and the time-to-event period is set at 45 days. An estimated reduction of time to platelet count response for subjects in the caplacizumab arm of 40% is assumed. With a median time to response in the placebo arm assumed to be

7 days, this would correspond with a median time to response in the caplacizumab arm of 4.2 days. In addition, an expected drop-out rate of 10% in the first 10 days after first administration of study drug is taken into account in the calculations. Based on these assumptions a total sample size of 132 subjects (121 events) will provide a power of 80%. A total sample size of 132 subjects will also provide approximately 83% power to detect a 20% reduction in the first key secondary endpoint, using a two-sided chi-squared test with a large sample approximation and a 5% significance level. This assumes an incidence of 30% and 10% in the placebo and caplacizumab arms, respectively.

Independent Data and Safety Monitoring Board (DSMB)

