4.2.2 Calculation of percentages

Missing values will not be included in the denominator count when computing percentages.

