4.3 Key Definitions and Labels

4.3.1 Definition of baseline

Baseline is defined as the last non-missing assessment before first administration of study drug.

For assessments with multiple parameters per subject (such as laboratory assessments), baseline will be determined per parameter individually. It is recognized that baseline assessments may thus come from more than one assessment and not just from the “baseline visit” assessment. Baseline will be calculated for each treatment period separately (double-blind treatment and open-label treatment). The assessment on Day 1 of the open-label treatment period, taken before first administration of open-label caplacizumab, will be taken as baseline value for the open-label part.

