4.3.4 Screening and follow-up visits

For analyses by visit, screening visits will be shown for each treatment group, not pooled. For subjects who have not switched to open-label caplacizumab after recurrence, follow-up visits will be shown for each treatment group, not pooled. For subjects who have switched to open-label caplacizumab after recurrence, follow-up visits will be shown pooled for subjects who received caplacizumab during the double-blind treatment period and for subjects who received placebo during the double-blind treatment period. See Section 4.3.6. for more details.

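### At Week 5 and follow-up, the SMMSE and neurological tables drop subjects who switched or died from their randomized arm and re-base switchers' SMMSE change at the recurrence

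*SAP*

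**What the plan says.** SAP 6.2.2 and Tables 14.2.1.4.1 to 14.2.1.4.3 present neurological symptoms, SMMSE values and SMMSE change on the ITT population. The visits are the first five days, Weeks 1 and 5 after daily PE, and both follow-up (FU) visits. These rules decide who appears in which column:

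- **Randomized columns.** SAP 4.3.6, on Caplacizumab and Placebo: "only data up to the switch are used in the analyses of these treatment groups".
- **Switchers at follow-up.** SAP 4.3.4: "follow-up visits will be shown pooled for subjects who received caplacizumab during the double-blind treatment period and for subjects who received placebo". They share one column whatever their initial arm.
- **Non-switchers at follow-up.** SAP 4.3.4: "For subjects who have not switched to open-label caplacizumab after recurrence, follow-up visits will be shown for each treatment group, not pooled".
- **Open-label baseline.** SAP 4.3.1: "The assessment on Day 1 of the open-label treatment period, taken before first administration of open-label caplacizumab, will be taken as baseline value". SAP 6.2.2 repeats this for SMMSE change: "For the OL Caplacizumab treatment group change from baseline is based on the Day 1 assessment of the open-label treatment period".
- **Missing values.** SAP 4.2.4 imputes nothing unless stated, and nothing is stated for these endpoints. SAP 4.2.2: "Missing values will not be included in the denominator count when computing percentages". Protocol 3.2.3.2 foresees no FU assessments after death. Protocol 3.4.3.4 scores an unconscious subject 0/30 but gives no rule for death.
- **Relapse during follow-up.** Protocol 3.1.1 covers this case, beginning "In case a subject has a first or subsequent TTP relapse after completing study drug treatment in the FU period". Study drug is not restarted, so there is no switch.

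For corticosteroid use (SAP 5.5.1) and for PE, ICU and hospital days (SAP 6.2.2), the SAP instead keeps subjects in their initial arm after the switch, as Caplacizumab + OL Caplacizumab and Placebo + OL Caplacizumab.

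**The concern.** The tables are labelled ITT, but at the later visits the randomized columns hold subjects selected on what happened after randomization. That selection is related to treatment: Protocol 1.2.5 expects fewer exacerbations on caplacizumab, and Protocol 1.1 links cognitive deficits to acute ischemia and recurrent episodes. If caplacizumab protects cognition partly by preventing exacerbations, the Week 5 arm columns remove that route.

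Re-basing adds to this. Open-label Day 1 is when the recurrence is being treated, so a return towards the earlier level reads as a gain, and the preceding fall is not in any arm's change score. The schedule offers little else. In the 30-day post-daily PE period, neurological and SMMSE assessments are scheduled only at Weeks 1 and 5, so after an exacerbation in between the next scheduled one is open-label Day 1. SAP 4.3.3 keeps unscheduled post-dose values out of descriptive statistics.

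At stake is how two secondary efficacy endpoints are read by arm after the acute phase.

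**Working it through.** **Inputs**

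- 132 subjects randomized 1:1, so 66 per arm (Protocol 3.1.1, SAP 3.2).
- Phase II, Protocol 1.2.4: "exacerbation during treatment of 8% (n = 3) for caplacizumab compared to 28% (n = 11) for placebo".
- Phase II, same section, any recurrence including 1-month follow-up: 11 placebo (28.2%) and 10 caplacizumab (27.8%). Group sizes follow: 11/0.282 = 39 and 10/0.278 = 36.
- Design rates for the first key secondary endpoint: 30% and 10%.
- L, the persistent loss in a switcher, is not in the documents and is varied as an assumption.

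**1. The plan's nearest figure.** No power is given for these endpoints. The closest stated figure is about 83% for the first key secondary. With pooled variance, the null SE is √(2 × 0.20 × 0.80/66) = 0.0696 and the alternative SE is √((0.21 + 0.09)/66) = 0.0674. Power = Φ((0.20 − 1.96 × 0.0696)/0.0674) = Φ(0.94) = 82.7%. The figure reproduces.

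**2. Who leaves the randomized columns**

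| Rates used | Placebo leaving | Caplacizumab leaving | Remaining |
|---|---|---|---|
| Phase II exacerbation, 28% and 8% | 66 × 0.28 = 18.5 | 66 × 0.08 = 5.3 | 47.5 and 60.7 |
| Design composite, 30% and 10% | 66 × 0.30 = 19.8 | 66 × 0.10 = 6.6 | 46.2 and 59.4 |

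The second row is only an upper guide, because the composite also counts TTP-related death and thromboembolic events. Other losses are not included.

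**3. Week 5.** Exacerbations fall within the 30 days after daily PE by definition, so they precede or coincide with this visit. Suppose non-switchers have the same mean m in both arms and switchers are lower by L.

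- All placebo subjects: 0.72m + 0.28(m − L) = m − 0.28L
- All caplacizumab subjects: 0.92m + 0.08(m − L) = m − 0.08L
- Difference by randomized arm: 0.20L
- Difference shown in the planned columns: m − m = 0

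| Assumed L, SMMSE points | 1 | 3 | 5 | 10 |
|---|---|---|---|---|
| Hidden difference in means | 0.2 | 0.6 | 1.0 | 2.0 |

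For an assumed excess in symptom prevalence among switchers of 10, 25 or 50 percentage points, the hidden difference is 2, 5 or 10 points.

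**4. Follow-up visits.** The 20-point gap does not carry over: 28.2% − 27.8% = 0.4 points. What differs is which recurrences are removed.

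| Phase II subjects | Placebo (39) | Caplacizumab (36) |
|---|---|---|
| Exacerbation on treatment (would switch and leave) | 11 | 3 |
| Recurrence only after treatment (would stay) | 11 − 11 = 0 | 10 − 3 = 7 |
| Left in the arm column | 28, no recurrers | 33, up to 7 recurrers (21%) |

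Scaled to this trial, 7/36 × 66 is about 13 caplacizumab recurrers kept, against about 18 placebo recurrers removed. This only illustrates the asymmetry. Phase II treated for 30 days after daily PE, whereas this trial allows an extension, and a relapse may fall after the visit in question. I put no points figure on it.

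**The case against.** The strongest reply is that these are descriptive endpoints outside the test hierarchy, that a pre-switch summary is a legitimate choice, and that Protocol 3.6.4.2 uses the same three groups for the first two key secondary endpoints. The descriptive status stands and limits the weight of the point. The analogy stands only in part. In those key secondaries the recurrence is itself the event and is counted in the arm before the switch. Here the outcome is status at a visit that comes after it.

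A reader might infer that every subject who recurred is left out. The documents do not say so. Relapses in the FU period do not lead to a switch and stay in their arm. Relapses during the extension come after the 30-day period, so their Week 5 data normally remain. A subject who dies after a visit is counted at that visit.

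A reader might also infer that a decline at recurrence appears nowhere, or is charged to no arm. That goes too far:

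- Actual open-label SMMSE values, including Day 1, are tabulated (Table 14.2.1.4.2), though pooled over arms.
- Re-basing touches only SMMSE change; symptom proportions have no baseline to reset.
- Neurological TTP events are summarized by group (SAP 3.3.2.2, 6.2.2). The double-blind period ends one minute before the first open-label dose (SAP 4.4.1) and events are placed by start time (SAP 7.1.1), so an event starting before that dose counts in the randomized arm.
- Deaths are tabulated by group, and Listing 16.2.3.4 shows each subject's symptoms and scores.

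None of this yields a by-arm SMMSE change or symptom proportion at Week 5 or follow-up that includes the switchers.

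Finally, a by-arm table mixes open-label caplacizumab into the placebo arm, and the open-label Week 5 visit falls later than the double-blind one. Both objections stand; the fix has to address the second.

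**Conclusion.** The point holds for subjects who switched or died before the visit, and for the by-visit tables. About 18 placebo and 5 caplacizumab subjects would leave their columns through a switch if Phase II on-treatment exacerbation rates recur. At Week 5 the hidden difference is about 0.20 × L, favouring placebo if L is a real loss. This rests on equal outcomes among non-switchers in the two arms and on a loss that persists to the visit.

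It is tempting to apply the same 20-point imbalance to the FU visits, or to take the 30% and 10% design rates as confirming it. Neither is supported: Phase II recurrence including follow-up was nearly equal, and the design rates describe a composite. At follow-up the defect is unequal removal of recurrers, of unknown size.

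Nor can one conclude that the trial says nothing about neurological protection. Days 1 to 5 are essentially unaffected, since a switch requires an earlier stop of daily PE and a recurrence. No type I error is involved. A supportive table is worth adding; the present ones need not be withdrawn.

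**What to change.** Keep the current tables. Add to SAP 6.2.2, for Week 5 and both FU visits, a supportive presentation by Caplacizumab + OL Caplacizumab and Placebo + OL Caplacizumab that:

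- computes SMMSE change from the double-blind baseline for every subject;
- uses all randomized subjects as the denominator for neurological symptoms, with separate rows for *died before visit* and *switched before visit*;
- states the visit mapping. For example, for a switcher with no double-blind Week 5 visit, take the assessment closest to the planned double-blind Week 5 date, open-label Day 1 included; for follow-up, use each subject's own first and final FU visits.

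The cost is SAP wording and a few table columns and rows, because the assessments are already scheduled and the group definitions already exist. The downside should be stated with the tables: open-label caplacizumab given to placebo switchers may dilute the arm difference, and switchers' FU visits fall later in calendar time.
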